Title: A Phase II Trial of Valproic Acid in Patients with Advanced Thyroid Cancers of Follicular Origin

Principal Investigator: [name].
EOB/CCR/NCI
[name]
[name]
[name]
[contact]
[contact]

Associate Investigators: [name]., EOB/CCR/NCI
[name]., DEOB/CES/NIDDK
[name], R.N., DEOB/CES/NIDDK

[name]., NMD/CC/NIH
[name]., BDMS/OCD/CCR/NCI
[name]., DEOB/CES/NIDDK
[name], PHARM/CC/NIH
[name]., EOB/CCR/NCI
[name]., EOB/CCR/NCI

[name]., EOB/CCR/NCI
[name], R.N.,
OCD/CCR/NCI

[name]., EOB/CCR/NCI

Referral Contacts:

[name], R.N., OCD/CCR/NCI

PRECIS

Background:

- Patients who have advanced differentiated thyroid cancers (Stage IV) have a five-year survival of only 25%. Clinically this results in more aggressive growth, metastasis, decreased or loss of iodine uptake in the tumor, and tumors that may be refractory to conventional treatment: surgical resection, radioactive iodine treatment and thyroid hormone for TSH suppression.
- In thyroid cancer, valproic acid, at clinically achievable concentrations, has an antiproliferative and differentiating effect.
- We hypothesize that valproic acid may inhibit proliferation and induce differentiation in thyroid cancer cells so that ^{131}I may detect residual disease and be more effective for radioiodine ablation of thyroid cancer cells of follicular cell origin.

Objectives:

- The primary goal of this study is to determine if valproic acid will have an antineoplastic and differentiation effect in patients with advanced and or metastatic thyroid cancer of follicular cell origin.

Eligibility:

- Unresectable advanced and or poorly differentiated thyroid cancers of follicular cell origin (excluding anaplastic and medullary thyroid cancer) that have no uptake (<1%) on radioiodine scan or are unresponsive to radioiodine therapy.
- Elevated serum thyroglobulin (Tg) level (>100ng/ml on thyroid hormone; >10ng/ml off thyroid hormone).

Design:

- This will be an open label phase II study to assess the efficacy of valproic acid therapy as an antiproliferative and differentiation agent in patients with incurable differentiated thyroid cancer (unresponsive and/or radioiodine negative and unresectable).
- Oral valproic acid will be administered to reach a therapeutic serum level (50 to 100 $\mu\text{g}/\text{ml}$).

1 INTRODUCTION

1.1 STUDY OBJECTIVES

- 1.1.1 To determine if valproic acid will inhibit thyroid cancer growth, as evidenced by a decrease in thyroglobulin level, and tumor size.
- 1.1.2 To determine if valproic acid therapy will induce differentiation of thyroid cancer cells and therefore increase uptake of radioactive iodine by the tumor cells.
- 1.1.3 To determine the effect of valproic acid on differentiation markers of thyroid cancer and global gene expression in thyroid tumor tissue.

1.2 BACKGROUND AND RATIONALE

Thyroid cancer is the fastest growing cancer diagnosis in the U.S.¹. Approximately 10-15% of patients present with aggressive disease and have about a 30% mortality rate at 5-10 years following initial treatment². Patients with stage IV differentiated thyroid cancer have a five-year survival of only 25%. In patients with progressive or recurrent differentiated thyroid cancer, one-third of patients develop or have dedifferentiated tumors (loss of differentiation)³. Clinically this results in more aggressive growth, metastasis, decreased or loss of iodine uptake in the tumor, and tumors that may be refractory to conventional treatment: surgical resection, radioactive iodine (RAI) treatment and thyroid hormone for TSH suppression. In addition, up to 20% of patients with differentiated thyroid cancer have evidence of residual disease as indicated by detectable serum thyroglobulin levels but have negative RAI scans⁴. Patients with differentiated thyroid cancer are usually treated after total or near total thyroidectomy with RAI (I-131) in order to ablate any residual thyroid tissue and/or cancer. Loss of iodine uptake makes RAI ablation therapy ineffective. Further dedifferentiation of thyroid cancers of follicular cell origin, in about 1% of patients, leads to the formation of anaplastic thyroid carcinoma, which is uniformly lethal.

Valproic acid, a histone deacetylase (HDAC) inhibitor, has long been used as an anticonvulsant to treat seizures in patients with epilepsy. It has also been used to treat bipolar disorder. Recent studies have shown that this class of drugs has promising effects in the treatment of cancer by inhibiting cancer cell proliferation, inducing apoptosis, cell cycle arrest and differentiation in brain, hematologic, endometrial, ovarian and prostate cancers⁵⁻⁸. Preclinical studies also suggest that valproic acid has a similar antiproliferative and differentiating effect in human thyroid cancer cells⁹⁻¹⁴.

Valproic acid interacts with the catalytic site of histone acetyltransferases to disrupt its activity. The post-translational modification process of acetylation is critical to gene transcription, with increased acetylation resulting in increased gene transcription. Because acetylation affects chromatin structure and nucleosomal packaging, it affects gene expression through this

mechanism. Approximately 2-5% of transcribed genes are significantly affected after treatment with HDAC inhibitors.

In thyroid cancer, valproic acid, at concentrations clinically achievable, has an antiproliferative and differentiating effect. At concentrations of 0.5 to 2.0mM, valproic acid inhibited growth by 55 to 80%⁹⁻¹⁴. Valproic acid also upregulates sodium-iodine symporter (NIS) gene expression in dedifferentiated thyroid cancer cells¹²⁻¹⁴. The NIS gene encodes the Na⁺/I⁻ symporter, located on the basolateral membrane of follicular thyroid cells and is responsible for iodide uptake. Downregulated NIS expression is the predominant mechanism of dedifferentiation in thyroid cancer cells of follicular cell origin that makes RAI ablation therapy ineffective. Treatment with valproic acid increases iodide accumulation in poorly differentiated thyroid cancer cells by increasing the expression of the NIS gene.

Patients with differentiated thyroid cancers are routinely followed with serial thyroglobulin (Tg) levels, ultrasonography and RAI scans. Recurrent or metastatic thyroid cancer of follicular cell origin is suspected by elevated serum Tg in the absence of RAI uptake on a diagnostic scan. Such "false negative" RAI scans occur in up to 20% of diagnostic RAI scans in patients with detectable Tg levels following thyroid ablation and positron emission tomography (PET) is helpful in only a subset of cases for detecting residual disease. The prognosis for patients with thyroid cancer is related to the ability of the cancer to accumulate RAI, since well-differentiated thyroid cancers usually respond to treatment with RAI.

We hypothesize that valproic acid may inhibit proliferation and induce differentiation in thyroid cancer cells so that ¹³¹I may detect residual disease and be more effective for radioiodine ablation of thyroid cancer cells of follicular cell origin (*excluding anaplastic and medullary thyroid cancer*). If our study demonstrates a tumor response to valproic acid by decreased tumor size and/or decreased thyroglobulin and/or increased radioiodine uptake in patients who are otherwise no longer amenable to conventional therapy, we will have data to support conducting a large, multicenter, trial using valproic acid.

We will also perform correlative studies in tumor tissue biopsy samples to directly determine an effect of valproic acid on differentiation markers, cell cycle and apoptosis regulatory genes, and genome-wide gene expression analysis.

1.3 STUDY DESIGN

This will be an open label phase II study to assess the efficacy of valproic acid therapy as an antiproliferative and differentiation agent in patients with incurable differentiated thyroid cancer (unresponsive and/or radioiodine negative and unresectable). Patients with advanced thyroid cancers of follicular cell origin who have failed conventional therapy (including total thyroidectomy, ¹³¹I ablation, with or without external radiation) who are thyroglobulin-positive/radioiodine-unresponsive will be eligible to enroll in this study. The intervention plan will be to administer valproic acid to all patients and then to compare serum thyroglobulin levels, radioiodine uptake and tumor size, by imaging studies, before and after therapy, as well as, perform correlative tumor tissue studies.

Valproic acid will be administered at an initial dose of 500 mg daily, titrating to 1500 mg daily by week 2 and continuing for 10 weeks. Patients will then undergo imaging for response. Depending on the response, patients will proceed to ablation, continue with an increased dose of valproic acid or be removed from treatment. This dose and dosing schedule was chosen to obtain a concentration level known to have an antineoplastic effect based on the fact that an oral dose of 500 mg twice daily should achieve plasma concentrations of valproic acid typically ranging from 0.4-0.6mM. Valproic acid serum trough levels will be obtained for all patients at the beginning of week 2 and then weekly thereafter to assess compliance, possible drug toxicity and to ensure plasma concentration is 50 to 100 μ g/ml.

We will perform tumor tissue biopsy of the target lesions in patients with tumor that is accessible to percutaneous biopsy by ultrasound or CT scan guidance. This will allow us to determine if valproic acid has effects on differentiation, cell cycle and apoptosis regulatory genes, as well as, genome-wide gene expression profile with valproic acid treatment. The correlative studies will then be evaluated based on response and therapeutic serum valproic acid levels. (Study Schema Appendix 1)

2 ELIGIBILITY ASSESSMENT AND ENROLLMENT

2.1 ELIGIBILITY CRITERIA

2.1.1 Inclusion Criteria

- 2.1.1.1 Advanced/poorly differentiated thyroid cancers of follicular cell origin that have no uptake (<1%) on radioiodine scan or are unresponsive to radioiodine therapy. Unresponsiveness to radioiodine therapy is defined as a patient's thyroglobulin not falling to less than 2ng/ml within 6 months after previous radioiodine ablative treatment.
- 2.1.1.2 Extensive (invasive) loco-regional tumor mass and/or metastatic spread, rendering patient inoperable
- 2.1.1.3 Thyroglobulin (Tg) levels greater than or equal to 100 ng/ml in the absence of Tg antibodies. Patients who are Tg-antibody (Tg-Ab) positive may be included despite a lower Tg level if they have detectable disease on cross sectional imaging. (The presence of Tg-Ab may lead to falsely low Tg levels and therefore render the Tg a less sensitive marker of disease. However, Tg-Ab has been shown to also act as a tumor marker, and will be used as an endpoint for the study in patients who are Tg-Ab positive.)
- 2.1.1.4 Within 18 months of enrollment, patients must have had an RAI scan, showing no or therapeutically insignificant RAI uptake ($\leq 1\%$).

2.1.1.5 Initial therapy must have included total/near-total thyroidectomy and RAI ablation therapy.

2.1.1.6 Patients must have had no chemotherapy, radiotherapy, or biologic therapy for their malignancy in the month prior to treatment and must have recovered from all side effects of therapeutic and diagnostic interventions.

2.1.1.7 Greater than or equal to 18 years of age

2.1.1.8 Must be able to understand and sign the Informed Consent Document

2.1.1.9 Clinical performance status of ECOG less than or equal to 1

2.1.1.10 Life expectancy of greater than three months

2.1.1.11 Women of childbearing potential must have a negative serum beta-HCG within 72 hours prior to study entry and must be willing to practice effective birth control to prevent pregnancy while receiving treatment and for three months after treatment is discontinued. All males of child fathering potential must also be willing to practice effective birth control.

2.1.1.12 Laboratory results must be within the following parameters before entry:

- Absolute Neutrophil Count > 750 cells/mm³
- Hemoglobin > 8.0 gm/dl
- Platelet count > 75000/mm³
- Creatinine < 1.5 times ULN
- Total protein > 6.4.
- Total bilirubin should be < 1.5 times ULN.
- AST (SGOT), ALT (SGPT) < 1.5 times ULN.
- Amylase < 1.5 times ULN
- Ammonia < 1.5 times ULN

2.1.2 Exclusion Criteria

2.1.2.1 Allergy to valproic acid.

2.1.2.2 Current coexisting malignancy other than basal cell carcinoma.

2.1.2.3 Women of child-bearing potential who are pregnant or breastfeeding. Valproic acid is a known teratogen, causing primary neural tube defects, facial abnormalities, and skeletal malformation; therefore pregnant women will be excluded. Additionally, patients that become pregnant while on study protocol will be discontinued immediately.

2.1.2.4 Active systemic infections, coagulation disorders or other major medical illnesses

2.1.2.5 Patients taking tolbutamide, warfarin, zidovudine, benzodiazapines, clonazepam, diazepam

2.1.2.6 Seizure disorder

2.1.2.7 Patients with brain metastases

2.2 RESEARCH ELIGIBILITY EVALUATION

Within 4 weeks prior to treatment

- Ultrasound of the neck
- MRI or CT of the Chest
- Bone scan for patients in whom bone metastases are suspected
- FDG PET scan
- Health Related Quality of Life HRQOL) form completion
- MRI of the brain

Within 2 weeks prior to treatment

- Laboratory Evaluations
 - Thyroid Stimulating Hormone (TSH)
 - Thyroglobulin (Tg)
 - CBC with differential and platelets
 - BUN, creatinine, total protein, total bilirubin, ALT, AST ALKP, amylase, ammonia, albumin
 - 24 hour urinary iodine level
 - Tumor biopsy
- Thyrogen (recombinant TSH) RAI scan (for radioiodine uptake and TSH stimulated thyroglobulin levels. See section 3.4)
- Complete history and physical examination including Height, Weight and ECOG status
- Tumor tissue biopsy of any accessible lesions

Within 3 days prior to treatment

- Serum or urine beta-HCG (if applicable)

2.3 REGISTRATION PROCEDURES

Authorized staff must register an eligible candidate with NCI Central Registration Office (CRO) within 24 hours of signing consent. A registration Eligibility Checklist from the web site (<http://home.ccr.cancer.gov/intra/eligibility/welcome.htm>) must be completed and faxed to [contact]. After confirmation of eligibility at Central Registration Office, CRO staff will call pharmacy to advise them of the acceptance of the patient on the protocol prior to the release of

any investigational agents. Verification of Registration will be forwarded electronically via e-mail to the research team. A recorder is available during non-working hours.

3 STUDY IMPLEMENTATION

3.1 STUDY DESIGN

Current conventional therapy for patients with thyroid cancers of follicular cell origin after thyroidectomy and ablative treatment with 131-I involves only thyroid hormone for TSH suppression. In this study, patients will receive TSH suppression therapy with valproic acid for 16 weeks.

The total study period will be 18 weeks, with a one year follow up. Patients who respond to treatment as evidenced by decreased Tg level, RAI uptake or decreased tumor size will continue treatment of valproic acid for 1 year.

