3.5 PHASE 2 WEEKS 11-16

3.5.1 Schedule 1 - Patients who exhibit an increased radioiodine uptake on Thyrogen scan post valproic acid therapy at week 10.

- Week 11:
 - Discontinue Levothyroxine
 - Begin Cytomel for 4 weeks (25 micrograms twice a day)
 - Continue valproic acid for a total of 16 weeks

Note: medication will be dispensed following review of Thyrogen scan
- Week 12 - may be performed by their primary physicians
 - Physical exam including ECOG status
 - CBC with differential, platelets, BUN, creatinine, total protein, total bilirubin, ALT, AST, ALKP, amylase, ammonia, albumin and b-HCG (if applicable).
 - Toxicity assessment, pill count, and review of diary
- Week 14: may be performed by their primary physicians
 - Physical exam including ECOG status
 - CBC with differential, platelets, BUN, creatinine, total protein, total bilirubin, ALT, AST, ALKP, amylase, ammonia, albumin and b-HCG (if applicable).
 - Toxicity assessment, pill count, and review of diary
 - Stop Taking Cytomel.
 - Begin low iodine diet.
- Week 16:
 - Measure TSH, Tg and 24 hour urinary iodine.
 - I-131 Ablative treatment {refer to Section 3.6}.
 - Physical exam including ECOG status
 - CBC with differential, platelets, BUN, creatinine, total protein, total bilirubin, ALT, AST, ALKP, amylase, ammonia, albumin and b-HCG (if applicable).
 - Toxicity assessment, pill count, and review of diary
- Week 17:
 - Post ablation RAI scan {5 days (+/- 2 days) following administration of 131-I}.
 - Ultrasound of the neck
 - MRI or CT of the neck and chest
 - FDG-PET scan
 - Resume Levothyroxine (pre study dose) .

- Stop valproic acid end of week 17
- Toxicity assessment, pill count, and review of diary
- Health Related Quality of Life HRQOL) form completion

3.5.2 Schedule 2 – patients who do not exhibit an increased radioiodine uptake on Thyrogen scan post valproic acid therapy at week 10

- Week 11:
 - Maintain valproic acid dose
- **Note:** medication will be dispensed following review of the Thyrogen scan.
- Week 12:
 - Physical exam including ECOG status
 - CBC with differential, platelets, BUN, creatinine, total protein, total bilirubin, ALT, AST, ALKP, amylase, ammonia, albumin and b-HCG (if applicable).
 - Serum valproic acid levels.
 - Toxicity assessment and review of diary
- Week 14: may be performed by local physician
 - Physical exam including ECOG status

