 - CBC with differential, platelets, BUN, creatinine, total protein, total bilirubin, ALT, AST, ALKP, amylase, ammonia, albumin and b-HCG (if applicable).
 - Toxicity assessment and review of diary
- Week 16:
 - Physical exam including ECOG status
 - CBC with differential, platelets, BUN, creatinine, total protein, total bilirubin, ALT, AST, ALKP, amylase, ammonia, albumin and b-HCG (if applicable).
 - Tg, TSH
 - Toxicity assessment and review of diary
 - Ultrasound of the neck and mediastinum
 - MRI or CT of the neck and chest
 - FDG-PET scan
 - Health Related Quality of Life HRQOL) form completion
- Weeks 17-52
 - Patients who show a response by RECIST criteria or have a decreased thyroglobulin level from Day 1 of the treatment (registered as a partial response to the treatment) will continue on valproic acid at their current dose for a total of 52 weeks.

- Stop valproic acid if no response
- Sixteen weeks or 4 months is significant amount of time to measure response to treatment and therefore, if there is a response, a patient's thyroglobulin levels should have decreased by then, as well as, by RECIST criteria.
- Patients who show no response, patients will stop valproic acid treatment and continue with routine follow up.

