3.8 FOLLOW UP FOR ALL PATIENTS {FROM WEEK 17}

- 3 months
 - Physical exam including ECOG status
 - CBC with differential, platelets, BUN, creatinine, total protein, total bilirubin, ALT, AST, ALKP, amylase, ammonia, albumin.
 - CT and/or MRI of the chest
 - Health Related Quality of Life HRQOL) form completion
 - Ultrasound of the neck as indicated
 - Tg, TSH
- 6 months
 - Physical exam including ECOG status
 - CBC with differential, platelets, BUN, creatinine, total protein, total bilirubin, ALT, AST, ALKP, amylase, ammonia, albumin..
 - Tg, TSH
 - Health Related Quality of Life HRQOL) form completion
- 9 months - for patients continuing on valproic acid only-
 - Physical exam including ECOG status
 - CBC with differential, platelets, BUN, creatinine, total protein, total bilirubin, ALT, AST, ALKP, amylase, ammonia, albumin.
 - Tg, TSH
 - Health Related Quality of Life HRQOL) form completion

- 12 months
 - Physical exam including ECOG status
 - CBC with differential, platelets, BUN, creatinine, total protein, total bilirubin, ALT, AST, ALKP, amylase, ammonia, albumin.
 - CT and/or MRI of the chest
 - Ultrasound of the and neck
 - Tg, TSH
 - Health Related Quality of Life HRQOL) form completion

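### Valproic acid duration for Schedule 1 patients is contradictory: 16 weeks, end of week 17, or 1 year, each with a passage behind it

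*Protocol*

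**What the plan says.** **Schedule 1 duration.**
- Protocol 3.1 gives a general duration: "patients will receive TSH suppression therapy with valproic acid for 16 weeks". It then adds that patients who respond "as evidenced by decreased Tg level, RAI uptake or decreased tumor size will continue treatment of valproic acid for 1 year".
- Schedule 1 (3.5.1) is defined by its entry condition: "Patients who exhibit an increased radioiodine uptake on Thyrogen scan post valproic acid therapy at week 10".
- The week-11 entry of 3.5.1 reads "Continue valproic acid for a total of 16 weeks". The week-17 entry of the same list reads "Stop valproic acid end of week 17". There is no branch for continuing beyond that.
- The continuation is carried out only in 3.5.2 (Schedule 2, weeks 17-52), where patients with a RECIST response or a fall in thyroglobulin "will continue on valproic acid at their current dose for a total of 52 weeks".

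**Follow-up clock.** Section 3.8 is headed "FOLLOW UP FOR ALL PATIENTS {FROM WEEK 17" and limits its 9-month visit to patients still on valproic acid.

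**Lesser points.**
- The design summary in 1.3 has some patients, depending on the week-10 response, go on at a higher valproic acid dose. Section 3.5.2 keeps the dose unchanged at week 11, and 3.4 only says treatment continues.
- Cytomel is given twice a day in 3.5.1 and once daily in 9.2.4.

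**The concern.** The protocol states no rule for which section takes precedence. Staff who stop a Schedule 1 patient at week 16, at the end of week 17 or at about one year can each point to a passage. Several things depend on the stop date:

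- **Exposure and time at risk.** The toxicity stopping rule in 3.2.4 runs over the whole treatment and follow-up period, so patients treated for different lengths of time would be pooled in it.
- **Adverse-event capture.** Under 5.1.1, from 30 days after the last treatment only events that are serious, unexpected and related enter the database.
- **Contraception.** Under 2.1.1.11 it runs for women until three months after treatment ends, and 2.1.2.3 describes the drug as a known teratogen.
- **The 9-month visit.** Section 3.8 reserves it for patients continuing the drug.
- **Week-17 assessments.** In Schedule 1 the neck and chest imaging and the post-ablation scan, "Post ablation RAI scan {5 days (+/- 2 days) following administration of 131-I", are listed at week 17. Whether the patient is still on drug then depends on which line of 3.5.1 is followed.

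**Working it through.** **Step 1: does 3.1 apply to Schedule 1?** The sentence in 3.1 lists RAI uptake between two items that carry the word decreased. Read as increased uptake, which is how 5.2 counts it toward response, every Schedule 1 patient meets the condition by definition. Read literally as decreased uptake, it would contradict 5.2. Even then, a Schedule 1 patient whose thyroglobulin or tumor size falls would come under the 1-year rule while 3.5.1 stops the drug. The conflict survives either reading.

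**Step 2: durations side by side (weeks of valproic acid, Schedule 1).**

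| Source | Duration |
|---|---|
| 3.5.1, week-11 entry | 16 |
| 3.5.1, week-17 entry | 17 |
| 3.1, responders (1 year taken as the 52-week total of 3.5.2) | 52 |

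Differences: 17 − 16 = 1 week; 52 − 17 = 35 weeks; 52 − 16 = 36 weeks. Ratios: 52/17 = 3.06; 52/16 = 3.25.

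**Step 3: what moves with the stop date.** This assumes that the last treatment in 5.1.1 means the last valproic acid.
- End of full adverse-event capture, 30/7 = 4.3 weeks later: about week 20.3, 21.3 or 56.3.
- End of contraception for women, three months = 3 × 52/12 = 13 weeks later: about week 29, 30 or 65.

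**Step 4: the 9-month visit.** 9 × 52/12 = 39 weeks. Counted from week 17, as the heading of 3.8 says: 17 + 39 = week 56. The continuation in 3.5.2 ends at 52 weeks in total, and 56 > 52. Taken literally, nobody following 3.5.2 is still on drug at the visit reserved for those on drug. It would fall within the 52 weeks (week 39) only if months ran from the start of treatment, which is not what the heading says. Who is meant to attend cannot be worked out from the text.

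**Step 5: the design figures in 6.2.** With 13 patients in stage 1 (stop if 0 responses) and at least 3 responses among 20 needed at the end, the probability of declaring efficacy is the sum over x = 1 to 13 of P(Bin(13, p) = x) × P(Bin(7, p) ≥ max(0, 3 − x)).
- p = 0.05: 0.0736 (stated: no more than 7.4%). Early stop 0.95^13 = 0.513 (stated: at least 51%).
- p = 0.25: 0.903 (stated: at least 90%). Early stop 0.75^13 = 0.0238 (stated: less than 2.5%).
- Enrolment: 20/0.80 = 25, as stated.

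All reproduce. Treatment duration is not an input to any of them.

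**Step 6: the lesser conflicts.**
- The trough-based titration in 3.2.3 does not reconcile 1.3 with 3.5.2, because it follows the serum level while 1.3 ties the increase to response. Section 1.3 gives no amount, so no exposure difference can be calculated.
- Over four weeks Cytomel would be given 2 × 28 = 56 times or 1 × 28 = 28 times. Section 9.2.4 gives no amount, so daily doses cannot be compared.

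**The case against.** The strongest reply is that 3.1 is a short overview and that the dated week-by-week list governs. On that view 16 weeks is the default and 1 year an extension written for Schedule 2 only. This makes 3.1 consistent with itself, but not with 3.5.1: 3.1 names RAI uptake as a ground for continuing, no precedence rule is stated, and the dated list itself gives two stop times. The pill count listed at week 17 hints at how that entry was meant, but it does not remove the week-11 instruction.

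A second reply is that one week is trivial. That largely stands. I-131 is given at week 16 under either reading, the post-ablation scan is not a response component in 5.2, and no effect of one week of drug on lesion size is shown.

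A third concerns the lesser points. Each sets a summary line or a pharmacy line against a single dated instruction, so staff working from the schedule meet one rule. This stands, and it is why they rank lower.

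A reader might also infer more than the text supports:
- **A 68-week course (16 + 52).** No passage says this. The one passage that carries out the continuation makes 52 weeks the total.
- **A biased response rate or altered error rates.** The week-10 uptake and thyroglobulin components precede every stop date, and the 35- to 36-week gap falls after the week-16 and week-17 assessments.
- **A measurable dose difference in Schedule 2 or for Cytomel.** The documents give no amounts from which to derive one. The dose conflict does cover weeks 11-16, before the 16-week lesion assessment, but no effect on that assessment is shown.

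**Conclusion.** The contradiction is real and lies in the current text. For every Schedule 1 patient, valproic acid may last 16, 17 or about 52 weeks. The 1-week gap is explicit within 3.5.1. The 35- to 36-week gap against 3.1 rests on two readings: RAI uptake in 3.1 means increased uptake, and 1 year means the 52-week total of 3.5.2.

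The consequences are for drug exposure, adverse-event capture, the contraception period and the 9-month visit, which as dated falls about 4 weeks after the 52-week total (56 − 52). Type I error, power, sample size and the week-10 response components are untouched. The dose conflict (1.3 against 3.5.2) and the Cytomel frequency conflict (3.5.1 against 9.2.4) are secondary, with no endpoint effect shown. This is more than clerical, because treatment and safety data depend on it, but it does not threaten the primary test.

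**What to change.** The sponsor should amend the text so that each item is stated once and consistently:

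1. Reconcile 3.1 with 3.5.1 on Schedule 1 valproic acid duration, including 16 weeks against the end of week 17 inside 3.5.1.
2. Make the 1 year in 3.1 agree with the 52-week total in 3.5.2, and make both agree with the 9-month visit in 3.8 as counted from week 17.
3. Reconcile 1.3 with 3.5.2 on the valproic acid dose from week 11.
4. Reconcile 3.5.1 with 9.2.4 on Cytomel frequency.

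Which duration, dose or frequency stands is a clinical decision for the sponsor, and none is proposed here. The cost is a text amendment. The reconciliation itself adds no patients, tests or visits. Further drug supply or 9-month visits for Schedule 1 patients would arise only if the sponsor keeps the 1-year text for them.
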